9.1 Hematological Toxicity – Dose Adjustment

NUC-1031 administration should be given according to the absolute neutrophil count (ANC) and platelet count on the day of dosing. On Day 1 of each 28-day cycle, if the ANC is $\geq 1.5 \times 10^9/l$ and the platelet count is $\geq 75 \times 10^9/l$, then NUC-1031 should be given at full dose unless the patient has previously been permanently dose reduced.

On Day 1 of each 28-day cycle, if the ANC is $1.5-1.0 \times 10^9/l$ and the platelet count is $50-75 \times 10^9/l$ without evidence of bleeding, then NUC-1031 should be given at a reduced dose unless the patient has received 2 prior dose reductions.

Within a cycle, should patients experience neutropenia or thrombocytopenia, dosing on Day 8 and Day 15 should be adjusted per [Table 2](#).

Table 2 Dose adjustments within a cycle (Days 8 and 15) based on ANC and platelet counts

ANC		Platelets	Starting dose (750 mg/m ²)	Starting dose (500 mg/m ²)	Starting dose (375 mg/m ²)
$\geq 1.5 \times 10^9/l$	AND	$\geq 75 \times 10^9/l$	750 mg/m ²	500 mg/m ²	375 mg/m ²
1.5-1.0 $\times 10^9/l$ and afebrile	AND/OR	50-75 $\times 10^9/l$ without evidence of bleeding	500 mg/m ²	375 mg/m ²	275 mg/m ²
$<1.0 \times 10^9/l$, or $<1.5 \times 10^9/l$ with fever	AND/OR	$<50 \times 10^9/l$, or $<100 \times 10^9/l$ with active bleeding	Omit	Omit	Omit

Should both the Day 8 and Day 15 doses be omitted for hematologic toxicity within the same cycle, the dose for all subsequent cycles should be permanently reduced to the next dose level.

If a patient starts a treatment cycle at 500 mg/m² and requires further dose reduction on Day 8 or Day 15 of the following cycle due to hematologic toxicity, dose modification should follow the column second from the right of [Table 2](#).

If a patient has her dose permanently reduced to 375 mg/m², and hematologic toxicity persists on any day that a dose is scheduled, dose modification should follow the far right column of [Table 2](#).

For all other hematologic toxicity, dose adjustments should be performed according to [Table 3](#).

Table 3 Dose adjustments for hematological toxicities (excluding toxicities relating to ANC and platelet counts)

NCI CTCAE grade	Dose adjustment
Grade 1 toxicity	If the patient was receiving 750 mg/m ² then reduce to 500 mg/m ² . If the patient was receiving 500 mg/m ² then reduce to 375 mg/m ² . If the patient was receiving 375 mg/m ² then reduce to 275 mg/m ² .
Grade 2, 3 and 4 toxicity	Omit until resolution to \leq Grade 1 if the patient was receiving 750 mg/m ² then resume at the dose 500 mg/m ² . If the patient was receiving 500 mg/m ² then resume at the dose 375 mg/m ² . If the patient was receiving 375 mg/m ² then resume at the dose 275 mg/m ² .

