4 PATIENT SELECTION

4.1 Inclusion Criteria

To be enrolled in this study, patients must meet the following criteria during the Screening period:

1. Provision of signed written informed consent. Patients with easily accessible tumor must also consent to the collection of fresh biopsy tumor tissue to participate in the study. Patients who do not have easily accessible tumor for biopsy should not be put at undue risk for sample collection and these patients remain eligible for the study.
2. Original diagnosis and/or histological confirmation of high-grade serous, high-grade endometrioid epithelial ovarian, fallopian tube or primary peritoneal cancer.
3. Platinum-free interval since last line of platinum of less than 6 months (182 days).
4. Received at least 3 prior chemotherapy-containing regimens. Prior treatment with only non-cytotoxic agents (*e.g.* hormones, antibodies or PARP inhibitors) is permitted, but should not be considered as one of the ‘3 prior chemotherapy-containing regimens’. Adjuvant chemotherapy should be counted as a prior line of therapy.
5. Age ≥ 18 years.
6. ECOG performance status of 0 or 1.
7. Measurable disease as defined by RECIST.
8. Adequate bone marrow function as defined by: absolute neutrophil count (ANC) $\geq 1.5 \times 10^9/l$, platelet count $\geq 100 \times 10^9/l$ and hemoglobin level ≥ 10.0 g/dl.
9. Adequate liver function, as defined by: serum total bilirubin $\leq 1.5 \times$ upper limit of normal (ULN), AST and ALT $\leq 2.5 \times$ ULN (or $\leq 5 \times$ ULN if liver metastases are present).
10. Adequate renal function assessed as Cr $< 1.5 \times$ ULN or GFR ≥ 50 ml/min.
11. Ability to comply with protocol requirements.

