9 DOSE MODIFICATIONS

Adverse events may be managed by dose delays and/or dose reductions according to the clinical situation. Advice on how to modify dosing for hematological and non-hematological toxicities is given below.

Only one dose reduction is permitted within a cycle. This may be a temporary dose reduction, in which case the next cycle can revert to the starting dose of the previous cycle, or it may be a permanent dose reduction which would apply to all subsequent cycles. Over the whole dosing period, each patient may have a maximum of 2 permanent dose reductions, after which treatment will be discontinued. The lowest dose which may be administered is 275 mg/m².

Treatment between cycles can be delayed for up to 14 days in order for patients to meet the re-treatment criteria before starting their next cycle. Patients who do not meet these requirements after this additional time will not be allowed to receive further cycles of NUC-1031 and will be withdrawn from the study.

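### Section 9.1 gives a Day 1 reduced-dose rule only when ANC and platelets are both mildly low; one mildly low count at 750 or 500 mg/m² has no Day 1 dosing rule

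*Protocol*

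**What the plan says.** Protocol Section 9.1 has two count-based rules for Day 1 (counts in 10⁹/l throughout).

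- **Full dose:** ANC at least 1.5 and platelets at least 75, subject to any earlier permanent reduction.
- **Reduced dose:** ANC 1.0–1.5 "and the platelet count is $50-75 \times 10^9/l$ without evidence of bleeding, then NUC-1031 should be given at a reduced dose". The exception for earlier reductions reads "should be given at a reduced dose unless the patient has received 2 prior dose reductions".

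The other parts of Sections 9 and 9.1 that bear on Day 1 are these.

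- Table 2 uses the same bands but joins the middle ones with *and/or*. It requires the patient to be afebrile on the ANC side, and it has an omit row. Its title is "Dose adjustments within a cycle (Days 8 and 15) based on ANC and platelet counts", and the sentence introducing it also limits it to Days 8 and 15.
- Table 3 is titled "Dose adjustments for hematological toxicities (excluding toxicities relating to ANC and platelet counts"), so it does not cover these counts.
- For a patient permanently reduced to 375 mg/m², if "hematologic toxicity persists on any day that a dose is scheduled, dose modification should follow the far right column of" Table 2. That covers Day 1 at this dose level only.
- Section 9 introduces the rules with "Advice on how to modify dosing for hematological and non-hematological toxicities is given below". It allows a delay of up to 14 days between cycles "in order for patients to meet the re-treatment criteria before starting their next cycle". A patient who still does not meet them receives no further cycles.
- Section 6.1 lists a delay of more than 14 days as a reason to stop, except where the patient is receiving clinical benefit.

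**The concern.** A dosing rule should not treat a milder toxicity more strictly than a worse one. With ANC 1.2 and platelets 60, both low, the Day 1 text gives a reduced dose. With ANC 1.2 and platelets 120, or ANC 2.0 and platelets 60, only one count is low and neither Day 1 rule applies. On Day 8 or 15 the same single low count would lead to a reduced dose under Table 2.

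Two things are at stake. The first is the individual patient: if the unmet Day 1 rules count as unmet re-treatment criteria, she waits up to 14 days and may lose further cycles. The second is consistency across about 30 planned sites: some may carry Table 2 over to Day 1 and others may follow the *and*, so that like patients are handled differently.

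The issue arises mainly from Cycle 2 onward, because inclusion criterion 8 in Section 4.1 ("Adequate bone marrow function as defined by: absolute neutrophil count (ANC") and what follows) requires ANC of at least 1.5 and platelets of at least 100 at screening.

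**Working it through.** No figure in the protocol needs reproducing. The check is to apply both sets of rules to every combination of bands.

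**Inputs, all from Section 9.1.** ANC bands: ≥1.5, 1.0–1.5, <1.0. Platelet bands: ≥75, 50–75, <50. The cycle is due at 750 or 500 mg/m², the patient has had fewer than 2 prior dose reductions, and fever and bleeding are set aside for the moment. Where Table 2's reduced and omit rows could both apply, because one count is in the lowest band, the omit row is taken.

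Each cell shows the Day 1 text, then Table 2:

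| | Platelets ≥75 | Platelets 50–75 | Platelets <50 |
|---|---|---|---|
| ANC ≥1.5 | full / full | **no rule / reduced** | no rule / omit |
| ANC 1.0–1.5 | **no rule / reduced** | reduced / reduced | no rule / omit |
| ANC <1.0 | no rule / omit | no rule / omit | no rule / omit |

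**Counts.**
- Day 1 text: 1 full + 1 reduced + 7 with no rule = 9.
- Table 2: 1 full + 3 reduced + 5 omit = 9.
- The 7 cells with no Day 1 rule split into 5 where Table 2 omits and 2 where Table 2 reduces.

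A delay in the 5 cells agrees with Table 2. The real disagreement is the 2 cells in bold.

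**Same-day dose in those 2 cells under Table 2.** From 750 mg/m²: 500/750 = 67%. From 500 mg/m²: 375/500 = 75%. If the Day 1 text is taken to mean delay, no dose is given that day.

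**Fever and bleeding.** Copying only Table 2's reduced row (*and/or* plus afebrile) into the Day 1 sentence would not be enough, because Table 2 relies on its omit row to catch these cases:
- ANC 1.2 with fever, platelets 60, no bleeding: the platelet condition alone is met, so she would be dosed. Table 2 omits.
- ANC 1.2 with fever, platelets 120: neither condition is met, so she still has no rule.
- ANC 1.2 without fever, platelets 60 with bleeding: the ANC condition alone is met, so she would be dosed. The present Day 1 sentence does not dose her, and Table 2 omits if the bleeding is active.

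The replacement wording therefore has to carry its own fever and bleeding conditions. With the wording given under the fix, the grid becomes 1 full, 3 reduced, 5 delay and 0 unmatched, and all three cases just listed are delayed.

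**The case against.** The strongest reply is that Section 9.1 does not say that a single low count on Day 1 means delay. It says nothing about that case. The delay comes from treating the undefined re-treatment criteria of Section 9 as these two sentences. Section 9 also calls its rules advice, to be applied according to the clinical situation. A sensible investigator who may give a reduced dose with two low counts will probably infer that one low count allows it too, and the intended meaning was probably *and/or*.

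Much of this stands. The delay is an inference, although the Day 1 sentences are the only count-based criteria for starting a cycle. Loss of further treatment needs several steps: a single middle-band count on Day 1, a site that follows the *and*, no recovery within 14 days, and no use of the clinical-benefit exception in Section 6.1. The nine-cell grid counts situations, not patients.

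What does not stand is the suggestion that the text therefore needs no change. Where the authors wanted Table 2 on every dosing day they said so, for 375 mg/m², and they did not say so for 750 or 500 mg/m². A stated dosing rule with the wrong conjunction is more than detail left to local judgement.

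**Conclusion.** The point holds as a drafting error in a dosing rule and should be corrected. At 750 or 500 mg/m², two of nine count combinations have no Day 1 dosing rule although Table 2 would give a reduced dose, and a combination with worse counts is dosed. That conclusion rests on the wording alone. The further step, that the single-low-count patient is delayed, rests on reading the Day 1 rules as the re-treatment criteria.

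A reader might infer more than the documents support:
- *Seven of nine combinations are mishandled.* Five of the seven have a count in the lowest band, where delay agrees with Table 2.
- *Patients with one mildly low count will be withdrawn after 14 days.* That is the upper-end outcome, and Section 6.1 allows continuation with clinical benefit.
- *Response rate, power or the choice of dose is affected.* The protocol does not say how often a single low count will occur on Day 1. Section 1.4.2 lists neutropenia and thrombocytopenia among the most common events in the Phase I study, which makes low counts foreseeable but gives no Day 1 frequency. No such effect can be claimed.

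Cycles at 375 mg/m² are outside the point, because Table 2 already applies to them on any scheduled day.

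**What to change.** Replace the Day 1 reduced-dose sentence in Section 9.1 with a rule of this content:

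- **Reduced dose:** ANC at least 1.0 and platelets at least 50, with at least one in the middle band (ANC 1.0 to <1.5, or platelets 50 to <75), provided there is no fever if ANC is <1.5 and no evidence of bleeding if platelets are <75. Keep the existing exception for 2 prior dose reductions.
- **Delay Day 1:** ANC <1.0, or platelets <50, or ANC <1.5 with fever, or platelets <75 with bleeding.

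Compared with the present text, this adds the two single-low-count cases to reduced dosing. It also newly delays the case of both counts in the middle band with fever, in line with Table 2. It does not newly permit dosing a bleeding patient with platelets below 75.

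One limit is left open on purpose. Table 2 also omits the dose when platelets are below 100 with active bleeding. Applying that on Day 1 would change the present full-dose rule for platelets 75–99, so it is a separate clinical decision for the sponsor. Until it is made, a patient with active bleeding and platelets 75–99 would be dosed on Day 1: at full dose if ANC is adequate, as now, and at the reduced dose if ANC is 1.0 to <1.5 without fever.

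The cost is one reworded sentence and one delay line, by amendment or clarification letter. There are no added procedures, visits or patients.

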9.2 Non-Hematological Toxicity – Dose Adjustment

Dose adjustment should be performed according to [Table 4](#). If dose omission is required, treatment should be delayed until the toxicity has resolved to \leq Grade 1. If this occurs, subsequent doses should be permanently reduced, without re-escalation. For significant pulmonary complications (*e.g.* pneumonitis and acute respiratory distress syndrome), study treatment should be stopped.

Table 4 Dose adjustment for non-hematological toxicities

NCI CTCAE grade	Dose adjustment
Grade 0-2 toxicity or Grade 3 nausea/vomiting/ alopecia	100% dose (with escalation of anti-emetic prophylaxis for nausea and vomiting)
Grade 3/4 toxicity (except nausea/vomiting/alopecia)	Omit until resolution to \leq Grade 1 if the patient was receiving 750 mg/m ² then resume at the dose 500 mg/m ² . If the patient was receiving 500 mg/m ² then resume at the dose 375 mg/m ² . If the patient was receiving 375 mg/m ² then resume at the dose 275 mg/m ² .

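### Section 9.1's Day 1 reduced-dose rule leaves out the fever condition that Table 2 applies to the same neutrophil band on Days 8 and 15

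*Protocol*

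**What the plan says.** Protocol Section 9.1 has two Day 1 sentences. The first gives full dose when ANC is at least 1.5 and platelets are at least 75 (all counts here ×10⁹/l). The second covers ANC 1.0 to 1.5 together with platelets 50 to 75: "without evidence of bleeding, then NUC-1031 should be given at a reduced dose unless the patient has received 2 prior dose reductions". Neither mentions fever.

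Table 2 in the same section applies to Days 8 and 15. Its reduced-dose row defines the ANC condition as "1.5-1.0 $\times 10^9/l$ and afebrile", and its omit row adds "or $<1.5 \times 10^9/l$ with fever" at every starting dose.

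Patients permanently reduced to 375 mg/m² whose haematological toxicity persists are sent to Table 2's far right column on any scheduled dosing day, which includes Day 1. Patients at 750 or 500 mg/m² are not.

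Section 9 introduces the rules permissively: "Adverse events may be managed by dose delays and/or dose reductions according to the clinical situation" and "Advice on how to modify dosing for hematological and non-hematological toxicities is given below". It also states: "Treatment between cycles can be delayed for up to 14 days in order for patients to meet the re-treatment criteria".

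**The concern.** The Day 1 sentence carries over three elements of Table 2's reduced-dose row (ANC band, platelet band, bleeding qualifier) and drops the fourth, fever. No reason is given for treating fever differently at the start of a cycle. The result is that the default instruction for a febrile patient with low neutrophils and low platelets is to give a myelosuppressive drug, when the sponsor's own table would withhold it in the same state one or two weeks later. On Days 8 and 15 the hold is an explicit rule; on Day 1 it depends on each investigator's judgement.

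The 375 mg/m² provision makes a deliberate difference hard to believe. With the same fever and counts on Day 1, the patient already at 375 mg/m² is held, while the patient at 750 or 500 mg/m² has a written default of treatment.

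What is at stake is patient safety and consistency between sites. No endpoint, sample size or error rate is involved.

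**Working it through.** The plan gives no figure to reproduce here. The check sets the two rules against each other over every combination of counts.

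**Inputs (Section 9.1).** Three ANC bands: at least 1.5; 1.0 to below 1.5; below 1.0. Three platelet bands: at least 75; 50 to below 75; below 50. The patient is not bleeding, has fewer than two prior reductions, and is on 750 or 500 mg/m².

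**Day 1 rule.** Full dose if ANC ≥1.5 and platelets ≥75; reduced dose if ANC is 1.0 to <1.5 and platelets are 50 to <75; otherwise hold, using Section 9's delay of up to 14 days. Fever plays no part.

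**Table 2 rule.** Omit if ANC <1.0, or platelets <50, or ANC <1.5 with fever; otherwise reduce if ANC is 1.0 to <1.5 or platelets are 50 to <75; otherwise full dose. Where two rows are met, the worse row applies.

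**Febrile patient** (Day 1 / Table 2):

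| ANC | Platelets ≥75 | 50 to <75 | <50 |
|---|---|---|---|
| ≥1.5 | full / full | hold / reduced | hold / omit |
| 1.0 to <1.5 | hold / omit | **reduced / omit** | hold / omit |
| <1.0 | hold / omit | hold / omit | hold / omit |

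Both full 1, both hold 6, Day 1 more cautious 1, Day 1 less cautious 1; 1 + 6 + 1 + 1 = 9.

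**Afebrile patient:**

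| ANC | Platelets ≥75 | 50 to <75 | <50 |
|---|---|---|---|
| ≥1.5 | full / full | hold / reduced | hold / omit |
| 1.0 to <1.5 | hold / reduced | reduced / reduced | hold / omit |
| <1.0 | hold / omit | hold / omit | hold / omit |

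Both full 1, both reduced 1, both hold 5, Day 1 more cautious 2, Day 1 less cautious 0; 1 + 1 + 5 + 2 + 0 = 9.

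**Result.** Over 18 cells, Day 1 is less cautious in 1 + 0 = 1 and more cautious in 1 + 2 = 3. With Table 2's dose steps, the less cautious cell is 500 against 0 mg/m² for a 750 mg/m² patient and 375 against 0 for a 500 mg/m² patient.

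**Does another rule force a hold in that cell?** No.
- The 14-day delay in Section 9 is for patients who do not meet the re-treatment criteria. This patient satisfies the Day 1 reduced-dose sentence.
- Table 4 (Section 9.2) omits only for Grade 3/4 toxicity. Grade 0-2 toxicity stays at full dose.
- Section 10.2 mentions febrile neutropenia only for growth-factor use.
- The exclusion for active infection needing IV antibiotics (Section 4.2) applies at Screening.
- Stopping for intercurrent illness (Section 6.1) is a matter of judgement.

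**After the change.** If febrile patients with ANC <1.5 are held on Day 1, the marked cell becomes hold / omit and the less cautious count is 0 of 18 at both doses. Afebrile patients are unaffected.

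**The case against.** The strongest reply is that there is no contradiction. The two rules govern different days, so no visit has conflicting orders. Section 9 calls its rules advice and allows delay, and Section 5.5.1 has the patient examined, with temperature taken, before the Day 1 infusion. Harm would need an investigator to see fever with two low counts and dose anyway. All of this stands. It limits the weight of the point, but a permitted hold is still weaker than a required one.

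Second, Table 2 joins its conditions with and/or, so platelets of 50 to 75 alone also satisfy its reduced-dose row, and the omission depends on the worse row winning. That reading is needed for the table to work at all: ANC below 1.0 with platelets 50 to 75 also meets both rows, and nobody would read that as permission to dose.

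Third, the Day 1 rule is stricter than Table 2 in 3 of the 18 cells and looser in only 1. That is true, but being stricter for other patients does not protect the febrile one. The cells are unweighted, so 1 in 18 is not a frequency.

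Finally, the case is rare. It needs fever, both counts in band, no bleeding, fewer than two prior reductions and a dose of 750 or 500 mg/m². Entry requires ANC of at least 1.5 and platelets of at least 100 (Section 4.1), so it arises mainly from Cycle 2 on. This is accepted.

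**Conclusion.** The concern holds. In one defined state the written Day 1 default is a reduced dose where Table 2 withholds the drug. It is an inconsistency between dosing days, most likely a drafting omission, and it should be corrected.

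The conclusion rests on three readings: that the worse row of Table 2 prevails, that the Day 1 reduction uses Table 2's steps, and that patients outside both Day 1 sentences are delayed under Section 9. It also reads the Day 1 condition literally, requiring both counts in band. If sites read it as and/or, as in Table 2, a febrile patient with ANC 1.0 to below 1.5 and platelets of at least 75 would also be dosed on Day 1 and omitted by Table 2, so the literal reading is the narrower one. The document gives no frequency for this state, and the number of patients affected cannot be estimated.

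**What to change.** In the Day 1 reduced-dose sentence of Section 9.1, add the afebrile condition after the ANC band. Then add a sentence along these lines: if ANC is below 1.5 × 10⁹/l with fever on Day 1, the start of the cycle is delayed, within the 14-day limit, at all dose levels.

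The cost is one phrase and one sentence in an amendment. No new procedure is needed, since temperature is already taken before Day 1 dosing (Section 5.5.1) and the delay window already exists (Section 9). The downside is an occasional short delay. In rare cases, a patient who has not recovered within 14 days would be withdrawn under Section 9, so the amendment should acknowledge that consequence.

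### Day 1 dosing rules leave out Table 2's omit criteria, Table 2 gives no order between its rows, and Sections 6.1 and 9 disagree on one group delayed more than 14 days

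*Protocol*

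**What the plan says.** All counts are in ×10⁹/l.

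**Day 1 (Section 9.1, text).** If ANC is ≥1.5 and platelets are ≥75, "then NUC-1031 should be given at full dose unless the patient has previously been permanently dose reduced". The dose is reduced "if the ANC is $1.5-1.0 \times 10^9/l$ and the platelet count is $50-75 \times 10^9/l$ without evidence of bleeding", unless two reductions have already been made. The full-dose rule mentions neither bleeding nor fever. The reduced-dose rule excludes bleeding but does not mention fever. Day 1 has no omit row.

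**Days 8 and 15 (Section 9.1, Table 2).** The table is titled "Dose adjustments within a cycle (Days 8 and 15) based on ANC and platelet counts". It has three rows:

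- Full dose: ANC ≥1.5 AND platelets ≥75.
- One level down: ANC "1.5-1.0 $\times 10^9/l$ and afebrile" AND/OR platelets 50–75 without bleeding.
- Omit: ANC "<1.0 \times 10^9/l$, or $<1.5 \times 10^9/l$ with fever" AND/OR platelets "<50 \times 10^9/l$, or $<100 \times 10^9/l$ with active bleeding".

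**Patients at 375 mg/m².** Once a patient has come down to this level for good, Table 2 governs every dosing day, Day 1 included: "hematologic toxicity persists on any day that a dose is scheduled, dose modification should follow the far right column".

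**Delay over 14 days.** Section 9 allows up to 14 days between cycles to meet the re-treatment criteria. A patient who still fails them gets no more cycles and is withdrawn, with no exception. Section 6.1 lists an AE delay of more than 14 days as a reason to stop, but exempts patients who are receiving clinical benefit.

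**The concern.** Table 2 shows which states the sponsor considers unsafe to dose. The Day 1 rules do not apply that judgement at the start of a cycle, so a site following them literally would infuse a cytotoxic drug in a state that Table 2's omit row covers. Within Table 2, some patients meet two rows at once and the table does not say which governs. For long delays, two sections give different answers for one group of patients.

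At stake are patient safety and consistent conduct across about 30 sites. Decreased neutrophil and platelet counts were among the most common treatment-related events in the Phase I study (Section 1.4.2), so the cytopenia rules will be used.

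**Working it through.** The plan states no figure here to reproduce. The check is a logical enumeration of the rules and does not measure impact.

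**Inputs.** All thresholds come from Section 9.1. I read 1.5–1.0 as 1.0 to <1.5, and 50–75 as 50 to <75.

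**States.** ANC {≥1.5; 1.0 to <1.5; <1.0} × platelets {≥100; 75 to <100; 50 to <75; <50} × fever {yes, no} × bleeding {yes, no} = 3 × 4 × 2 × 2 = 48.

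**Step 1: Day 1 as written.**

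- Full dose: ANC ≥1.5 with platelets in either of the two upper bands, whatever the fever and bleeding status: 2 × 2 × 2 = 8 states.
- Reduced dose: ANC 1.0 to <1.5, platelets 50 to <75, no bleeding, with or without fever: 2 states.
- Total dosed: 8 + 2 = 10. Three of these meet Table 2's omit criteria:

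| ANC | Platelets | Fever | Bleeding | Day 1 | Table 2 rows matched |
|---|---|---|---|---|---|
| ≥1.5 | 75 to <100 | no | yes | full | full, omit |
| ≥1.5 | 75 to <100 | yes | yes | full | full, omit |
| 1.0 to <1.5 | 50 to <75 | yes | no | reduced | reduce, omit |

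In the first two states the Day 1 dose is 750 or 500 mg/m². In the third it is 500 or 375 mg/m², if a reduced dose means one Table 2 level (an assumption).

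**Step 2: Table 2 overlaps.** The 2 bleeding states above match both full dose and omit. Seven more match both reduce and omit, because AND/OR lets one count select the reduce row while the other selects omit:

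| ANC | Platelets | Fever | Bleeding |
|---|---|---|---|
| 1.0 to <1.5 | 75 to <100 | no | yes |
| 1.0 to <1.5 | 50 to <75 | no | yes |
| 1.0 to <1.5 | 50 to <75 | yes | no |
| 1.0 to <1.5 | <50 | no | no |
| 1.0 to <1.5 | <50 | no | yes |
| <1.0 | 50 to <75 | no | no |
| <1.0 | 50 to <75 | yes | no |

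**Step 3: single low counts on Day 1.** Five states match only the reduce row of Table 2 but neither Day 1 rule. Three have ANC 1.0 to <1.5 alone: platelets ≥100, afebrile, with or without bleeding (2 states), and platelets 75 to <100, afebrile, no bleeding (1). Two have platelets 50 to <75 alone: ANC ≥1.5, no bleeding, with or without fever. These patients fall to the Section 9 delay, while a patient with both counts low is dosed.

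**Step 4: the 14-day rules side by side.**

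| Patient after more than 14 days' delay for an AE | Section 9 | Section 6.1 |
|---|---|---|
| Still fails re-treatment criteria, no clinical benefit | no further cycles | stop |
| Still fails re-treatment criteria, clinical benefit | no further cycles | may continue |

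The conflict is confined to the second line.

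**Step 5: testing the repair.** If the most restrictive matching row governs, Table 2 gives 6 full, 6 reduced and 36 omit, with one instruction in every state. With the same omit criteria as Day 1 delay criteria, no Day 1 state that meets them is dosed. The five single-low-count states then depend on the choice about *and*:

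| Day 1 choice | Full | Reduced | Delay by omit criteria | Single low count |
|---|---|---|---|---|
| Keep *and* | 6 | 1 | 36 | 5 fall to delay |
| Change to *and/or*, afebrile | 6 | 6 | 36 | dosed (5 of the 6 reduced) |
| Delay both groups | 6 | 0 | 36 | 5 delayed, as is the 1 with two low counts |

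The delay criteria are needed. Adding a bleeding condition to the full-dose rule, *and/or* and an afebrile condition without them would still dose 7 states that meet the omit criteria, for example ANC 1.2 with platelets 40.

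**The case against.** **The rules are guidance under clinical supervision.** Section 9 lets AEs be managed by delay or reduction according to the clinical situation, and says "Advice on how to modify dosing for hematological and non-hematological toxicities is given below". Section 5.5 requires medical review on dosing days. An investigator may therefore withhold drug from a bleeding or febrile patient, which softens the harm. It does not remove it: the Day 1 text says drug should be given where the protocol's own omit criteria apply. Table 4 does not fill the gap, because it omits only at Grade 3/4 and gives 100% dose at Grade 0–2. The 375 mg/m² provision does not cover patients at 750 or 500 mg/m².

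**Table 2 is sensibly read as omit.** The bleeding limb would have no effect at platelets 75 to <100, with ANC ≥1.5, unless it overrode the full-dose row. This is fair. A reader might infer that Table 2 orders full dose for that patient, and it does not: she matches both rows. What is missing is a statement of which governs. The febrile state in Step 1 also matches two rows, so it is right to say that the omit row covers it, but not that omit is Table 2's only answer.

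**Single low counts.** A reader might infer that these patients are put at risk on Day 1. They are not, because the Section 9 delay withholds drug. Nor is changing *and* to *and/or* a mere wording correction: it would dose patients who are now delayed. Day 1 may differ from Table 2 by intent, although dosing two low counts while holding one is hard to explain as a stricter rule.

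**Conclusion.** The point holds as a safety and consistency defect in Sections 9.1, 9 and 6.1, and should be corrected.

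- Day 1, read literally, doses 3 of 48 states that meet Table 2's omit criteria. Clinically these are two situations: bleeding with platelets 75 to <100, and fever with both counts moderately low.
- Table 2 matches two conflicting rows in 2 + 7 = 9 states.
- Sections 6.1 and 9 conflict for one group only: patients who still fail the re-treatment criteria after 14 days and have clinical benefit.

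This rests on a literal reading, the band boundaries stated above, and patients not already at 375 mg/m². State counts are not patient frequencies, and the protocol gives none. Entry requires ANC ≥1.5 and platelets ≥100 (Section 4.1), so the problem mainly concerns doses after the first. A reader might infer that ORR or dosing intensity is distorted; nothing in the document shows this.

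**What to change.** 1. **Day 1.** Apply Table 2's omit criteria as delay criteria: ANC <1.0, or <1.5 with fever; platelets <50, or <100 with active bleeding.
2. **Table 2.** State that the most restrictive matching row applies.
3. **Delays over 14 days.** Use one rule in Sections 6.1 and 9, either by carrying the clinical-benefit exception into Section 9 or by removing it from Section 6.1. The medical team should choose.
4. **Day 1 *and*.** The medical team should decide between *and/or* with an afebrile condition, which loosens Day 1 dosing, and delaying both groups. The choice should be recorded as clinical.

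The cost is a protocol amendment to three sections, with the ethics and regulatory approvals that Section 15.4 requires. Sample size, endpoints and analysis do not change.
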